4.2 Dose Modifications

4.2.1 Dose Interruptions

Clinically indicated dose interruptions of JAK-I are permitted for up to 14 days. If a treatment break continues for greater than 14 days the patient will need to withdraw from study.

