7 STATISTICAL CONSIDERATIONS

7.1 Sample Size and Power Calculation

This is a single arm phase Ib pilot study to evaluate the effect of Itacitinib in 25 patients with advanced HCC. The two primary outcomes for this study are safety and tolerability as well as overall response rate. The study will be powered on overall response rate as per the below. A trials steering committee will convene every 6 months to review safety and clinical data.

The Simon's minimax two-stage design will be used where the null hypothesis that the clinical benefit rate (CBR) is 0.05 will be tested against a one-sided alternative, defining the maximum unacceptable activity (p_0) for the experimental treatment as an overall response rate of 5% (33,34). Assuming the experimental treatment is able to achieve a minimal acceptable activity (p_1) of at least 25% of overall response rate so that the null hypothesis can be rejected, i.e. to test the alternative one-sided hypothesis with 90% power that the overall response rate (p_1) is greater than p_0 , at least 4 or more response patients with clinical benefit will have to be reported among the final sample size of 25 patients. In accordance with the Simon's minimax two-stage design, an interim comparison of activity will be conducted in the first stage at complete assessment of the primary efficacy endpoint for the first 15 patients accrued. For a 20% difference in response rate CBR (5% v 25%), at least 1 patient with overall response should have been observed among the first 15 patients. If there are 0 responses in these 15 patients, the study will be stopped. Otherwise, 10 additional patients will be accrued for a total of 25 and a second comparison will be made on the final sample size. This design yields a one sided type I error rate of 0.05 and power of 0.90 when the true response rate is 0.25.

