7.2 Analysis Plan

The clinical data will be entered and stored in InForm™ database. Statistical analysis will be conducted using R version 3.0.1 and Stata version 14.

One interim analysis is planned as described above for the efficacy primary endpoint. A final analysis will be conducted at the end of the study. Analyses will include an intent to treat analysis including all patients enrolled and a per protocol analysis using all patients who complete the study without major protocol violations.

Histograms and boxplots will be used to check the distribution and possible outliers for continuous variables. Continuous variables that follow a normal distribution will be summarised using means and standard deviations. Skewed continuous variables will be summarised using medians and inter-quartile ranges. Categorical variables will be summarised using frequencies and percentages.

A separate statistical analysis plan will be prepared and finalised prior to database lock. Any deviation(s) from the final statistical plan in the final analysis will be described and justification will be given in the final report.

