7.2.1 Analysis Plan

Due to sample size constraints, for the primary outcomes of assessing the safety and tolerability of Itacitinib and overall response rate, we will use descriptive measures such as frequencies and percentages.

All patients who receive at least one dose of study treatment will be included in the safety analysis set. The frequency of adverse events (AEs) will be assessed for severity (NCI CTCAE v4.03), expectedness, seriousness and causal relationship to study drugs(s). In addition, AEs will be summarised by toxicity type, impact on study drug(s) and by timing.

All efficacy data in the study will be analysed on an intention-to-treat (ITT) basis, regardless of treatment received. To be considered 'evaluable' for the primary efficacy analysis, a patient must have a week 8 tumour assessment or evidence of disease progression or death prior to week 8.

For quality of life measures, both means and standard deviations for continuous variables as well as frequencies and percentages for categorical variables will be used.

For the translational / exploratory endpoints, appropriate descriptive measures as well as univariate models will be shown as dependent on whether the relevant measure is categorical or continuous, whether the test is paired or not and whether is it normally or non-normally distributed as indicated below. Translational endpoints may not be included in the Clinical Study Report.

Univariate models will be performed for all demographic and other study variables, as statistically appropriate, as well as to test for confounding due to sample size constraints, with models such as Fisher's exact test or the Chi-square test utilised for categorical variables and t-tests or the Wilcoxon test (if the continuous variable does not follow a normal distribution) for continuous ones. For all estimates, 95% confidence intervals will be calculated.

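### The primary ORR denominator is contradictory: section 7.2.1 requires ITT, then limits the primary analysis to evaluable patients, so early treatment failures without a week-8 scan can be left out

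*Combined protocol and SAP*

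**What the plan says.** Three statements bear on who is counted in the primary ORR.

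- **ITT.** Section 7.2 describes the intent-to-treat analysis as covering every enrolled patient. Section 7.2.1 states: "All efficacy data in the study will be analysed on an intention-to-treat (ITT) basis, regardless of treatment received".
- **Evaluable patients.** For the primary efficacy analysis, the next sentence of 7.2.1 sets an evaluability condition: "a patient must have a week 8 tumour assessment or evidence of disease progression or death prior to week 8".
- **Accrued patients.** Section 7.1 places the interim look "at complete assessment of the primary efficacy endpoint for the first 15 patients accrued", stops at 0 responses in those 15, otherwise accrues 10 more to a total of 25, and requires at least 4 responders. It says: "This design yields a one sided type I error rate of 0.05 and power of 0.90 when the true response rate is 0.25".

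Section 7.2 also plans "a per protocol analysis using all patients who complete the study without major protocol violations". That is an additional analysis beside ITT and is not itself at fault, but it does not settle the primary denominator.

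Other sections decide who will lack a week-8 scan. Section 4.2.1 says: "If a treatment break continues for greater than 14 days the patient will need to withdraw from study". The notes to Table 1 (section 3.4.1) run tumour assessments every 8 weeks until progression or withdrawal, and give an end-of-treatment scan only if the last one was more than 4 weeks earlier. Section 4.2.3, by contrast, lists reasons for withdrawal from study treatment.

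Nowhere do the documents say whether a non-evaluable patient is replaced, counted as a non-responder or removed.

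**The concern.** All enrolled, all accrued and all evaluable patients are the same set only if nobody stops early without a scan. The evaluability rule keeps early progression and early death as failures, which is right. It has no place for a patient who stops before week 8 because of toxicity, a break of more than 14 days or withdrawn consent, and who has neither progressed nor died. Such a patient has not responded and should count as a failure.

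This missingness is informative. The patients at risk of removal include those who could not tolerate the drug, in a study whose other primary endpoint is tolerability. Removing them can only raise the ORR. ORR is the endpoint on which the study is sized and on which it may stop after stage 1. The interim wording adds a second ambiguity: if one of the first 15 accrued never has a complete assessment, it is unclear whether the look takes place on 15 accrued or 15 evaluable patients.

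**Working it through.** **Inputs.** From section 7.1: p0 = 0.05, p1 = 0.25, n1 = 15, stop at 0, n = 25, success at 4 or more, no allowance for non-evaluable patients. From section 7.2.1: 95% confidence intervals for all estimates (method not stated; exact Clopper-Pearson assumed here). The non-evaluable proportion q is not given; q = 10%, 20% and 30% is an assumed range. Response means complete or partial response.

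**1. Reproduce the design.** With X1 ~ Bin(15, p) and X2 ~ Bin(10, p):

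P(success) = Σ over x = 1, 2, 3 of P(X1 = x) × P(X2 ≥ 4 − x), plus P(X1 ≥ 4).

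- p = 0.05: 0.3658 × 0.0115 + 0.1348 × 0.0861 + 0.0307 × 0.4013 + 0.0055 = 0.0336.
- p = 0.25: 0.0668 × 0.4744 + 0.1559 × 0.7560 + 0.2252 × 0.9437 + 0.5387 = 0.901.

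A search over all two-stage designs confirms 0/15 and at least 4/25 as the minimax solution. The stated 0.05 is the ceiling; the attained alpha is 0.0336.

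**2. Effect on the estimate.** Lower limit = Beta quantile 0.025 (x, n − x + 1); upper limit = Beta quantile 0.975 (x + 1, n − x). With x = 4:

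| Denominator | ORR | Exact 95% CI |
|---|---|---|
| 25 (all accrued) | 16.0% | 4.5 to 36.1 |
| 22 (3 dropped) | 18.2% | 5.2 to 40.3 |
| 20 (5 dropped) | 20.0% | 5.7 to 43.7 |

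The responders are the same four people in each row. The lower limit moves above 5% only because non-responders were removed.

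**3. Effect on the decision, same accrued patients, no replacement.** Both boundaries are counts (0, and at least 4). Removing non-responders changes neither count, so go/no-go is identical and alpha remains 0.0336.

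**4. Effect if patients are replaced until 25 are evaluable.** Assume a true rate of 5% over all enrolled and no responses among non-evaluable patients. The rate among evaluable patients is then 0.05/(1 − q), put into the formula of step 1:

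- q = 10%: 0.0556, alpha 0.047
- q = 20%: 0.0625, alpha 0.067
- q = 30%: 0.0714, alpha 0.098

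**5. Effect if the boundary is rescaled.** 4/25 is 16%. With 18 evaluable, 0.16 × 18 = 2.88, so 3 responses would suffice, and P(X ≥ 3 | 18, 0.05) = 0.058 (single-stage), above 0.05.

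**6. Power with all accrued patients counted.** If 25% holds over all enrolled, power stays 0.901. If 25% holds only among evaluable patients and the rest never respond, the rate per accrued patient is 0.25 × (1 − q):

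- q = 10%: 0.225, power 0.843
- q = 20%: 0.200, power 0.762
- q = 30%: 0.175, power 0.655

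By step 3, these figures apply equally to the current count rule without replacement.

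**The case against.** The strongest reply is that 7.2.1 defines evaluable but never says that the others are excluded. Section 7.2 commits to all enrolled patients, section 7.1 counts accrued patients, and a separate SAP is promised. This stands in part: exclusion is the natural meaning of a condition for the primary efficacy analysis, but it is not spelled out. Leaving it to the later SAP does not resolve it, because that document is due only before database lock. The 0/15 decision comes earlier, and responses in a single-arm study will be known by then.

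A reader might go further and infer that the Simon cut-offs no longer apply, that type I error is inflated, or that the 90% power is lost. The documents do not support this. The cut-offs are counts; the alpha figures in step 4 need a replacement rule that the protocol does not contain, and even then 10% non-evaluable stays under 0.05. Power falls only if the 25% target is taken to apply to evaluable patients alone, and the fix does not recover that loss.

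A reader might also add clinical deterioration without imaging to the patients who drop out. Section 4.2.3 pairs deterioration with disease progression, and 7.2.1 does not require progression to be radiological, so these patients may well count as evaluable failures.

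Two provisions narrow the gap. An end-of-treatment scan more than 4 weeks after the last one may show progression, which makes the patient evaluable. Section 8.3 keeps patients given alternative treatment in the study for follow-up and analysis. Neither covers a patient withdrawn from the study under 4.2.1, without progression, before week 8.

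Finally, 4/25 meets the success rule although its two-sided 95% CI includes 5%, because the test is one-sided at 0.05. The CI shift therefore affects how the result is reported, not the formal decision.

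**Conclusion.** The point holds as a contradiction over the primary denominator and the handling of missing week-8 assessments. Read naturally, 7.2.1 removes patients who stop early for toxicity, a long break or withdrawn consent without a scan, progression or death. At the success boundary this raises the reported ORR from 16.0% to 18.2% with three dropped and to 20.0% with five, and lifts the lower confidence limit past the 5% null.

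The formal go/no-go result and the attained alpha of 0.0336 are unaffected while the rule is a count in the same accrued patients. Alpha inflation is conditional on replacement or rescaling, and the 10% to 30% range for non-evaluable patients is assumed. The contradiction itself and the upward direction of the bias in the ORR depend on none of these assumed rates.

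**What to change.** - **Section 7.2.1:** define the primary ORR denominator as all enrolled patients, namely the first 15 at stage 1 and 25 at the end, without replacement. Count any patient without a week-8 complete or partial response as a non-responder. Keep the evaluable set as a sensitivity analysis.
- **Section 7.1:** use the same wording for the interim look, so that a patient among the first 15 with no assessment is counted rather than awaited or replaced.
- **Sections 4.2.1, 4.2.3 and the notes to Table 1:** reconcile withdrawal from study, the end of scanning at withdrawal, and withdrawal from study treatment, so that patients who stop treatment stay in follow-up for the scheduled week-8 assessment if they consent. The 14-day limit itself is not in question.

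The cost is wording, to be settled before the stage 1 look, and a slightly lower reported ORR. If the 25% target was meant for evaluable patients only, power is about 84%, 76% or 66% at 10%, 20% or 30% non-evaluable. That is the same as under the present count rule without replacement, so the sponsor should state which population the 25% refers to.

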8 REGULATORY ISSUES

8.1 CTA

This study has Clinical Trials Authorisation from the UK Competent Authority; MHRA.

8.2 Ethics Approval

The Study Coordination Centre has obtained approval from the Yorkshire & The Humber - Sheffield Research Ethics Committee (REC) and Health Regulator Authority (HRA). The study must also receive confirmation of capacity and capability from each participating NHS Trust before accepting participants into the study or any research activity is carried out. The study will be conducted in accordance with the recommendations for physicians involved in research on human subjects adopted by the 18th World Medical Assembly, Helsinki 1964 and later revisions

8.3 Consent

Consent to enter the study must be sought from each participant only after a full explanation has been given, an information leaflet offered and time allowed for consideration. Signed participant consent should be obtained. The right of the participant to refuse to participate without giving reasons must be respected. After the participant has entered the trial the clinician remains free to give alternative treatment to that specified in the protocol at any stage if he/she feels it is in the participant's best interest, but the reasons for doing so should be recorded. In these cases the participants remain within the study for the purposes of follow-up and data analysis. All participants are free to withdraw at any time from the protocol treatment without giving reasons and without prejudicing further treatment.

8.4 Confidentiality

Participants' identification data will be required for the registration process. The Study Coordination Centre will preserve the confidentiality of participants taking part in the study and is registered under the Data Protection Act.

8.5 Indemnity

Imperial College London holds negligent harm and non-negligent harm insurance policies which apply to this study.

8.6 Sponsor

Imperial College London will act as the main Sponsor for this study. Delegated responsibilities will be assigned to the NHS trusts taking part in this study.

8.7 Funding

Incyte Corporation are funding this study

8.8 Audits And Inspections

The study may be subject to inspection and audit by Imperial College London under their remit as Sponsor, the Study Coordination Centre and other regulatory bodies to ensure adherence to GCP.

9 STUDY MANAGEMENT

The day-to-day management of the study will be co-ordinated through Hammersmith Cancer Research Office.

10 PUBLICATION POLICY

The results will be published once the study is complete

Appendix A: Inhibitors and inducers of P450 CYP 3A4

| Precipitant | Therapeutic Class | Object ^a (oral, unless otherwise specified) | AUC _{ratio} | PMID or NDA # | Published |
|---|-------------------------------|--|----------------------|--------------------------|-----------|
| Potent CYP3A Inhibitors (yielding substrate AUCr > 5) | | | | | |
| indinavir /RIT | Protease Inhibitors | alfentanil | 36.5 | 19225389 | 2009 Mar |
| tipranavir/RIT | Protease Inhibitors | midazolam | 26.91 | 20147896 | 2010 June |
| ritonavir | Protease Inhibitors | midazolam | 26.41 | 20002087 | 2009 Dec |
| cobicistat (GS-9350) | None | midazolam | 19.03 | 20043009 | 2010 Mar |
| indinavir | Protease Inhibitors | varidenafil | 16.25 | NDA # 021400 | 2003 Aug |
| ketoconazole | Antifungals | midazolam | 15.9 | 8181191 | 1994 May |
| troleandomycin | Antibiotics | midazolam | 14.8 | 15536460 | 2004 Dec |
| saquinavir / RIT | Protease Inhibitors | midazolam | 12.48 | 19792991 | 2009 Oct |
| itraconazole | Antifungals | midazolam | 10.8 | 8181191 | 1994 May |
| voriconazole | Antifungals | midazolam | 9.63 | 21937987 | 2011 Nov |
| telaprevir | Antivirals | midazolam | 9.17 | NDA # 201917 | 2011 |
| mibefradil | Calcium Channel Blockers | midazolam | 8.86 | 14517191 | 2003 Oct |
| clarithromycin | Antibiotics | midazolam | 8.39 | 16432272 | 2006 Feb |
| lopinavir / RIT | Protease Inhibitors | aplaviroc | 7.71 | 16934050 | 2006 Sep |
| elvitegravir / RIT | Treatments of AIDS | midazolam IV | 6.8 | 18815591 | 2009 Jan |
| posaconazole | Antifungals | midazolam | 6.23 | 19302901 | 2009 Feb |
| nelfinavir | Protease Inhibitors | simvastatin | 6.07 | 11709322 | 2001 Dec |
| telithromycin | Antibiotics | midazolam | 6.0 | NDA# 021144 | 2004 |
| grapefruit juice DS ² | Food Products | midazolam | 5.95 | 12953340 | 2003 Aug |
| conivaptan | Diuretics | midazolam | 5.76 | NDA # 021697 | 2005 |
| nefazodone | Antidepressants | midazolam | 5.44 | 14551182 | 2003 Nov |
| saquinavir | Protease Inhibitors | midazolam | 5.18 | 10430107 | 1999 Jul |
| boceprevir | Antivirals | midazolam | 5.05 | NDA # 202258 | 2011 |
| Moderate CYP3A Inhibitors (AUCr ≥ 2 and < 5) | | | | | |
| fluconazole | Antifungals | midazolam | 4.93 | 16172184 | 2005 Oct |
| atazanavir / RIT | Protease Inhibitors | maraviroc | 4.9 | 18333863 | 2008 Apr |
| darunavir | Protease Inhibitors | saquinavir | 4.9 | NDA # 021976 | 2006 |
| erythromycin | Antibiotics | midazolam | 4.42 | 8453848 | 1993 Mar |
| diltiazem | Calcium Channel Blockers | midazolam | 4.06 | 21209240 | 2011 Nov |
| darunavir / RIT | Protease Inhibitors | sildenafil | 4.0 | NDA # 021976 | 2006 |
| dronedaron | Antiarrhythmics | simvastatin | 3.66 | NDA # 022425 | 2009 |
| atazanavir | Protease Inhibitors | maraviroc | 3.57 | 18333863 | 2008 Apr |
| aprepitant | Antiemetics | midazolam | 3.29 | 12891225 | 2003 Aug |
| casopitant | Antiemetics | midazolam | 3.13 | 20840445 | 2010 Oct |
| amprenavir | Protease Inhibitors | rifabutin | 2.93 | 11158747 | 2001 Feb |
| imatinib | Antineoplastic Agents | simvastatin | 2.92 | 14612892 | 2003 Nov |
| verapamil | Calcium Channel Blockers | midazolam | 2.92 | 8198928 | 1994 Mar |
| grapefruit juice | Food Products | midazolam | 2.39 | 10546919 | 1999 Oct |
| tofisopam | Benzodiazepines | midazolam | 2.36 | 17989974 | 2008 Jan |
| cyclosporine | Immunosuppressants | midazolam | 2.21 | 21753749 | 2011 Sep |
| ciprofloxacin | Antibiotics | sildenafil | 2.12 | 16372380 | 2005 Dec |
| schisandra sphenanthera | Herbal Medications | midazolam | 2.05 | 19552749 | 2009 May |
| cimetidine | H-2 Receptor Antagonists | midazolam | 2.02 | 6152615 | 1984 Sep |
| FK1706 | Central Nervous System Agents | midazolam | 2.01 | 19889885 | 2010 Feb |
| Weak CYP3A Inhibitors (AUCr ≥ 1.25 and < 2) | | | | | |
| tabimorelin | Hormone Replacement | midazolam | 1.93 | 12610745 | 2003 Feb |
| ranolazine | Cardiovascular Drugs | simvastatin | 1.89 | NDA # 021526 | 2006 |
| fosaprepitant (IV) | Antiemetics | midazolam | 1.76 | 21209230 | 2011 Dec |
| Seville orange juice | Food Products | felodipine | 1.76 | 11180034 | 2001 Jan |
| chlorzoxazone | Muscle Relaxants | midazolam | 1.68 | 11736864 | 2001 Nov |
| M100240 | Antihypertensive Agents | midazolam | 1.66 | 15051745 | 2004 Apr |
| fluvoxamine | Antidepressants | midazolam | 1.66 | 14551182 | 2003 Nov |
| ranitidine | H-2 Receptor Antagonists | midazolam | 1.66 | 6135440 | 1983 Jun |

| Precipitant | Therapeutic Class | Object ¹ (oral, unless otherwise specified) | AUC _{ratio} | PMID or NDA # | Published |
|---|--|--|----------------------|--------------------------|------------|
| Weak CYP3A Inhibitors (AUCr ≥ 1.25 and < 2) (continued) | | | | | |
| goldenseal | Herbal Medications | midazolam | 1.63 | 17495878 | 2008 Jan |
| clotrimazole | Antifungals | midazolam | 1.61 | 20233179 | 2010 Feb |
| tacrolimus | Immunosuppressants | midazolam | 1.61 | 21753749 | 2011 Sep |
| cilostazol | Antiplatelets | lovastatin | 1.56 | 10702889 | 1999 |
| peppermint oil | Food Products | felodipine | 1.55 | 12235445 | 2002 Sep |
| roxithromycin | Antibiotics | midazolam | 1.47 | 7995324 | 1994 |
| propiverine | Anticholinergics | midazolam | 1.46 | 16183781 | 2005 Dec |
| isoniazid | Antibiotics | triazolam | 1.46 | 6140941 | 1983 Dec |
| oral contraceptives | Oral contraceptives | triazolam | 1.44 | 6149030 | 1984 Nov |
| delavirdine | NNRTIs | indinavir | 1.44 | 9665503 | 1998 Jul 1 |
| atorvastatin | HMG CoA Reductase Inhibitors (Statins) | midazolam IV | 1.41 | 12911366 | 2003 Sep |
| tolvaptan | Vasopressin Antagonists | lovastatin | 1.41 | NDA # 022275 | 2009 |
| linagliptin | Dipeptidyl Peptidase 4 Inhibitors | simvastatin | 1.34 | 20497745 | 2010 June |
| resveratrol | Food Products | buspirone | 1.33 | 20716633 | 2010 Sept |
| lacidipine | Calcium Channel Blockers | simvastatin | 1.33 | 11259986 | 2001 Feb |
| cranberry juice | Food Products | midazolam | 1.33 | 19114462 | 2009 Mar |
| pazopanib | Kinase Inhibitors | midazolam | 1.32 | 20881954 | 2010 nov |
| nilotinib | Kinase Inhibitors | midazolam | 1.3 | NDA # 020068 | 2007 |
| AMD070 | Fusion Inhibitors | midazolam | 1.29 | 18362694 | 2008 Apr |
| alprazolam | Benzodiazepines | buspirone | 1.29 | 8300893 | 1993 Nov |
| amlodipine | Calcium Channel Blockers | simvastatin | 1.28 | 16097365 | 2005 Mar |
| bicalutamide | Antiandrogens | midazolam | 1.27 | 15509184 | 2004 |
| sitaxentan | Endothelin Receptor Antagonists | sildenafil | 1.27 | 20078609 | 2010 Jan |
| azithromycin | Antibiotics | midazolam | 1.27 | 8720318 | 1996 Feb |
| ginkgo | Herbal Medications | midazolam | 1.25 | 17050793 | 2006 Nov |

| Inducers | Object (oral, unless otherwise specified) | % ↓ AUC | % ↑ oral CL | Precipitant Regimen (oral) | Published | PMID or NDA# |
|--|---|--------------|--------------|--|-----------|--------------------------|
| Potent Inducers (AUC decreased by ≥ 80% or CL increased by more than 5 fold (400%)) | | | | | | |
| rifampin | budesonide | 99.7 | 36904.5 | 600 mg QD (7 days) | 2005 | 15726657 |
| mitotane | midazolam | 94.5 | Not Provided | maximum of 3.5 g TID (chronic therapy) | 2011 | 21220434 |
| avasimibe | midazolam | 93.5 | Not Provided | 750 mg/day (7 days) | 2003 | 12766253 |
| phenytoin | nifedipine | 89.5 | Not Provided | 200-450 mg/day (chronic treatment) | 1996 | 8917062 |
| carbamazepine | quetiapine | 86.6 | 643.1 | 200 mg TID (26 days) | 2006 | 16390352 |
| St John's Wort | midazolam | 80.0 | Not Provided | 300 mg TID (14 days) | 2006 | 16341856 |
| rifabutin | delavirdine | Not Provided | 458.0 | 300 mg QD (14 days) | 1997 | 9224961 |
| phenobarbital | verapamil | 76.6 | 400.9 | 100 mg QD (21 days) | 1968 | 3392664 |
| Moderate Inducers (AUC decreased by 50-80% or CL increased by 2-5 fold (100-400%)) | | | | | | |
| ritonavir and St. Johns wort | midazolam | 77.2 | Not Provided | ritonavir: 300 mg BID and SJW: 300 mg TID (14 days) | 2010 | 19924124 |
| tipranavir and ritonavir | saquinavir | 75.6 | Not Provided | tipranavir: 500 mg and ritonavir: 200 mg BID (14 days) | 2008 | 18176328 |
| bosentan | sildenafil | 69.0 | 239.8 | 62.5-125 mg BID (8 weeks) | 2005 | 15963102 |
| naftillin | nifedipine | 62.6 | 145.1 | 500 mg 4 times daily (5 days) | 2003 | 12814453 |
| [talvireline] | indinavir | 61.7 | 181.2 | 500 mg TID (14 days) | 1999 | 10516944 |
| efavirenz | simvastatin acid | 60.4 | Not Provided | 600 mg QD (15 days) | 2005 | 15980690 |
| modafinil | triazolam | 57.6 | 35.7 | 200-400 mg QD (28 days) | 2002 | 11823757 |
| etravirine | sildenafil | 56.7 | Not Provided | 800 mg BID (13.5 days) | 2008 | NDA# 022187 |
| Weak Inducers (AUC decreased by 20-50% or CL increased by less than 2 fold (100%)) | | | | | | |
| garlic | saquinavir | 44.7 | Not Provided | caplet of GarlPure BID (20 days) | 2002 | 11740713 |
| amprenavir | lopinavir | 43.0 | Not Provided | 700 mg BID (2-4 weeks) | 2005 | 15668538 |
| [troglitazone] | simvastatin | 37.7 | Not Provided | 400 mg QD (24 days) | 2001 | 11361054 |
| sorafenib | sirolimus | 36.9 | Not Provided | 200 mg BID (11 days) | 2010 | 21045832 |
| rufinamide | triazolam | 36.7 | 53.4 | 400 mg BID (11.5 days) | 2008 | NDA # 021911 |
| [pleconaril] | midazolam | 34.6 | 52.8 | 400 mg TID (6 days) | 2006 | 16467135 |
| ginkgo | midazolam | 33.7 | 52.6 | 120 mg BID (28 days) | 2008 | 18205997 |
| vinblastine | midazolam IV | 33.2 | 48.8 | not provided (4 cycles) | 2010 | 20959500 |
| nevirapine | indinavir | 32.5 | Not Provided | 200 mg QD (14 days), then BID (19 days) | 1999 | 10191212 |
| armodafinil (R-modafinil) | midazolam | 32.2 | 54.7 | 100-250 mg/day (31 days) | 2008 | 18076219 |
| prednisone | tacrolimus | 29.0 | Not Provided | 1.5 mg/kg/day | 2005 | 15787787 |
